10.6.2.2 Phase 2: Pilot Actual Recruitment and Study Initiation

On training phase 2, on a **Monday** and **Tuesday**, the actual study will begin in a slow-motion pilot with recruitment at a reduced rate. Only one volunteer parent/participant will be recruited into the study each morning and each afternoon of **Monday** and **Tuesday** only, with actual blood collection, blinded vaccinations,

HIRRC/CDC Needle-free Intradermal	Page 90	File: 4785-ID-INF-Prot-Engl-2008Jun24.doc
Influenza Study - CDC-ISO-4785	of 138	2008-Jun-24

laboratory processing and all other study procedures. At any time when conditions dictate, the investigators may suspend further recruitment until readiness resumes. These four pilot phase 2 participants will return for their 2 day visits on **Wednesday** and **Thursday**, respectively, and for their remaining visits in future weeks, as per protocol.

Extra time will be spent assessing the parent diaries for correctness of completion and revising the parent-training process to overcome any problems detected. Each afternoon of the training phase 2 week, the investigators and other study personnel will meet to discuss problems and develop solutions. On **Friday**, a decision will be made whether and how much to increase the recruitment rate for the following week, and to add the remaining vaccination day of Wednesdays.

10.6.3 Screening and Recruitment

Recruitment and screening of participants will occur in the following steps. There will be no posters or public announcements.

A. The nurses who staff the Healthy Children and Vaccination Service [immunization clinic] of the hospital will identify eligible children among those in their waiting room by examining their visitor log and questioning parents. Eligibles will be patients or their accompanying siblings who are age 6 to 24 months and up-to-date with the national immunization schedule. (These nurses, in alternating morning and afternoon shifts, will serve as the study nurses who will handle logistics in the study center and will be trained to administer unblinded the study vaccinations.)

B. Parent(s) or guardian(s) (hereafter referred to by the singular "parent" but including the plural) of potential eligibles will be invited to consider participation of their child in an influenza vaccination study. The parent will be informed that non-interest or non-participation will not in any way affect the services they came to receive in the clinic.

C. If the parent expresses interest in the study, or asks technical questions that the nurses cannot easily answer, the parent and child will be escorted or directed to the Clinical Investigations Consultant's office, room 33, second floor.

D. There, the investigator physician will fully explain the study verbally, as detailed in the study information document, which the parent will be requested to read, as well.

E. If participation is declined, the parent will be thanked for their time and interest and escorted or directed with the child back to the ground floor Healthy Children and Vaccination Service [immunization clinic], where they will be attended to, if needed, or resume their original position in the queue.

F. If participation is desired, the investigator will interview the parent to determine that the child fulfills all the inclusion criteria and none of the exclusion criteria for participation. If not currently eligible due to age or recent vaccination, a return date

HIRRC/CDC Needle-free Intradermal	Page 91	File: 4785-ID-INF-Prot-Engl-2008Jun24.doc
Influenza Study - CDC-ISO-4785	of 138	2008-Jun-24

will be selected for their return, and the parent and child escorted or directed back to the immunization clinic, where they will resume, if needed, their original position in the queue. If permanently ineligible, this will be explained to the parent, who will be thanked for her time and interest and escorted or directed back to the immunization clinic, where they will resume, if needed, their original position in the queue.

G. To ensure compliance with the inclusion and exclusion criteria of the protocol and Part 4 of the Case Report Form (CRF), duplicate verifications will be required. First, the physician investigator who originally collects the demographic and clinical history in CRF Parts 2 and 3 will certify eligibility in question 30 of the CRF Part 4. Second, a different physician investigator will review the data to independently verify and certify eligibility of the child for the study in question 31, and duly sign in field 32.

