10.3.2 Exclusion Criteria

To be excluded are infants WHOSE PARENT(S)/LEGAL GUARDIAN(S) ... :

- a. are unable or unwilling to give written informed consent for their infant to participate in the study
- b. cannot be contacted by telephone (family's own or a neighbor's) by the study nurse if necessary for surveillance of adverse events if scheduled followup return appointments are not fulfilled
- c. are unable to complete the diary form for adverse events, to measure and record temperature with the TraxIt[™] skin-appliqué thermometer, to measure the maximal diameter of local reactions or limb circumference, or have difficulty reading or understanding written instructions, or other factors which indicate exclusion in the judgment of the study staff

Also to be excluded are INFANTS who ... :

- d. have fever (by parental report or by rectal temperature ≥38.5° C or axillary ≥38.0°
 C) currently or within the past 3 days, or who are currently suffering from an acute or chronic infectious disease (including known HIV)
- e. have had an acute or chronic infection requiring systemic antimicrobial therapy (antibiotic or antiviral) or other prescribed treatment within the past 21 days. This includes any underlying illness that may limit their response to vaccination, such as those receiving intravenous immunoglobulin for agammaglobulinemia, or systemic steroid therapy
- f. are malnourished, defined by weight less than two standard deviations below the median weight for their age
- g. are allergic to eggs, or have a history of any anaphylactic shock, asthma, urticaria, or other allergic reaction after previous vaccinations, or have allergy or hypersensitivity to any component of the study vaccine
- h. have ever received previously any influenza vaccine
- i. have received within the prior 28 days, or for whom there is the indication to receive in the next 56 days, any non-study vaccination or investigational agent outside of the study (This would exclude infants "behind schedule" and needing to receive on the day of first interview protection against tuberculosis, polio, diphtheria, tetanus, pertussis, hepatitis B, *Haemophilus influenzae* type b, measles, mumps, or rubella. See section 10.4.7 for the effect on recruited age ranges)
- j. have a known bleeding diathesis, or any condition that may be associated with a prolonged bleeding time
- k. have currently any serious confirmed or suspected disease, such as metabolic, cardiac, or autoimmune disease, or diabetes

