10.4.4 Method of Assigning Participants to Treatment Groups

For each phase of the study (I and II), an independent, outside party (e.g., a member of the Data and Safety Monitoring Board - DSMB) will determine in advance the injection method to be used for each participant identification (ID) number to be assigned in the study:

• IM-NS-0.25 (control)	(intramuscular, needle-syringe, full dose)
• IM-NS-0.1	(intramuscular, needle-syringe, reduced dose)
• ID-JI-0.1	(intradermal, jet injector, reduced dose)

The outside party shall provide copies of these treatment group assignments for each study ID number to at least two [other] members of the DSMB. These records shall remain confidentially in their custody in separate locations outside of the Dominican Republic and released only at the time and in the manner as described in this protocol.

A study nurse will assign permanent participant ID numbers consecutively to each patient in the chronological order in which the corresponding informed consent form is signed and he or she is enrolled.

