10.4.4.4 Allocation Group Randomization Envelopes

The outside, independent party shall prepare four (quadruplicate) sets of *allocation* group randomization envelopes. The envelopes shall be sealed, opaque, and not permit visualization of its contents upon holding up to the light. For each set, consecutive participant ID numbers shall be written, printed, or stickered clearly on the outside of each envelope, e.g., "CDC-ISO-4785 – **001**", "CDC-ISO-4785 – **002**", etc.

Three sets of envelopes, the GREEN, YELLOW and RED sets shall be provided to the Dominican Principal Investigator for use in the study injection room for the FIRST, SECOND, and THIRD study injections, respectively. They shall be marked on their covers "1 - Primera", "2 - Segunda", and "3 - Tercera",

HIRRC/CDC Needle-free Intradermal	Page 72	File: 4785-ID-INF-Prot-Engl-2008Jun24.doc
Influenza Study - CDC-ISO-4785	of 138	2008-Jun-24

respectively. (Envelopes for the RED set for the "insurance" dose will contain the IM full-dose randomization card shown in **Figure 16** for the two reduced-dose groups IM-NS-0.1 and ID-JI-0.1. RED envelopes for the full-dose group, IM-NS-0.25, having already received the standard 2-dose regimen, will contain a card indicating a mock injection, as shown in **Figure 19**.).

A fourth set of envelopes, the BLUE set, similarly identified on their outside by the participant's study ID number, shall be kept sealed in a secure location (e.g., locked safe) in the custody of the director of the HIRRC. The individual BLUE envelope for a specific participant shall be opened only upon the application of the Dominican Principal or Senior Investigators in the event of a serious adverse reaction for which treatment will depend upon knowledge of the vaccination method (IM-NS-0.25, IM-NS-0.1, or ID-JI-0.1) received by that participant.

The *allocation group randomization envelope* shall be opened by the unblinded injection nurse only when she and the other unblinded study staff (holding assistant) are all in the injection room with the participant of corresponding ID number, and his or her parents have left the room temporarily.

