10.6.2 Training of Study Personnel

Training for Dominican study personnel will be conducted in two stages lasting one week each. In addition, U.S. investigators and trainers from the jet injector manufacturer will be present during relevant periods of this training. Dominican study staff include 5 registered nurses, 3 auxiliary nurses, 3 physicians, one resident in pediatrics, one data/files manager, one laboratory professional, one laboratory technician, and 3 auxiliary nurses.

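### Nurses who find and invite families also give the unblinded injections; with fixed blocks of six, this leaves room for selective or delayed invitation

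*Protocol*

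**What the plan says.** Recruitment (section 10.6.3). The nurses who staff the immunization clinic "will identify eligible children among those in their waiting room by examining their visitor log and questioning parents", and they invite the parents. Step A adds that the same people, who work mornings and afternoons in turn, "will serve as the study nurses who will handle logistics in the study center and will be trained to administer unblinded the study vaccinations". The section describes no advertised way in: "There will be no posters or public announcements".

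Allocation (section 10.4.4 and its subsections). "A study nurse will assign permanent participant ID numbers consecutively to each patient in the chronological order" of consent and enrolment, and the number determines the envelope. The envelopes are sealed and opaque. Each "shall be opened by the unblinded injection nurse only when she and the other unblinded study staff" are in the injection room with the child. Assignments come in blocks of six, two per arm (10.4.4.1, repeated in 10.8.3). Against block counting, the first block alone is cut at a random point and its remainder is moved to the end of the list (10.4.4.2).

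Separation of roles (section 10.4.6). Unblinded staff are kept out of assessing and recording adverse events. No section keeps them out of finding or inviting families.

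Physicians (sections 10.6.3 D, F and G, and 10.6.4 A). The investigator explains the study, checks the criteria and takes consent, and a second physician certifies eligibility. Section 10.4.6 says that investigators are blinded.

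Staffing (section 10.6.2). "Dominican study staff include 5 registered nurses, 3 auxiliary nurses, 3 physicians", among others. No separate recruiting nurse is named.

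**The concern.** A sealed envelope hides the next card, but not what past cards imply about it when blocks have a fixed size. Concealment therefore also needs the people who decide whom to approach, and when, to be ignorant of past allocations. Here the people at the first step of recruitment may be the ones who opened the preceding envelopes.

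A nurse with a view on the jet injector, or on the reduced dose, could hold back or bring forward the invitation of a particular child, even without meaning to. Children of different age or robustness could then collect in different arms. Sections 10.4.4 and 10.8.3 describe no stratification by age, and age decides whether the thigh or the deltoid is injected. In phase I, with 16 children per arm, an excess of three to five events over control removes an arm from phase II (section 10.10), so a small shift in who enters which arm could matter.

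**Working it through.** The protocol gives no figure for predictability, so there is none to reproduce. The check asks how much a fully informed observer could know about the next allocation.

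**Inputs.** Blocks of six, two per arm (10.4.4.1, 10.8.3). First block cut into 1+5, 2+4, 3+3, 4+2 or 5+1 (10.4.4.2). Target of 450 entries. Assumption: the observer knows the block size, which the protocol states, and has seen or been told every past allocation.

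**Distinct orders of one block.** 6!/(2! × 2! × 2!) = 720/8 = 90. Section 10.4.4.1 gives 36 (3! × 3!). That slip does not affect this point, and the 90 orders are used below.

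**Predictability by position, block boundary known.**

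- Certain: the last place always is. The fifth is certain when the two remaining cards are for the same arm, with probability 3/C(6,2) = 3/15 = 1/5.
- Best guess: the largest remaining count divided by the number of cards left, averaged over the 90 orders. For the fourth place, the three remaining cards are one per arm with probability 8/20 = 0.4 and otherwise two and one, so 0.4 × 1/3 + 0.6 × 2/3 = 0.533.
- Jet arm used up before place k: C(k−1, 2)/15.

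| Place | Certain | Best guess right | Jet arm used up |
|---|---|---|---|
| 1 | 0 | 0.333 | 0 |
| 2 | 0 | 0.400 | 0 |
| 3 | 0 | 0.500 | 0.067 |
| 4 | 0 | 0.533 | 0.200 |
| 5 | 0.200 | 0.600 | 0.400 |
| 6 | 1 | 1 | 0.667 |
| Mean | 1.2/6 = 0.200 | 3.367/6 = 0.561 | 1.333/6 = 0.222 |

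An observer who saw no past allocations would be right one time in three and never certain.

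**Effect of splitting the first block.** The split moves the block boundary once, and every later block still has six places. In 2,000 simulated sequences, an observer who saw every allocation located the boundary after a median of 14 entries (95th percentile 27, maximum 47). In a further simulation over 450 entries, about 87 allocations were certain (87/450 = 19.4%, against 20.0% with no split) and 56.0% were guessed correctly. Against a fully informed observer, the split therefore gains almost nothing.

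**From prediction to selection.** The text gives this sequence: nurse identifies and invites (10.6.3 A, B); physician explains, screens and obtains consent (10.6.3 C to F, 10.6.4 A); second physician certifies (10.6.3 G); number follows the order of consent (10.4.4); injection nurse opens the envelope (10.4.4.4). The nurse's influence lies in the first step only. The later checks apply to children already referred, so they cannot reveal an eligible child who was passed over or invited later.

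**The case against.** The nurses do not enrol anyone. Parents consent, and blinded physicians apply the criteria, take consent and certify eligibility twice. The link from an invitation to a particular slot is also loose. Exclusion i bars children vaccinated in the previous 28 days or due a vaccine in the next 56, and children waiting in a vaccination clinic may often fail it. Section 10.6.3 F gives children not yet eligible a later return date, and other parents decline. Predicting the next card is therefore not the same as steering a chosen child to it. Full knowledge would need memory or sharing across shifts, because cards are destroyed and no record of dose or route is kept in the clinic. All of this stands, and it makes the figures upper bounds.

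Four stronger readings are tempting, and the documents support none of them:

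- *The nurses control who enters next.* They influence who is invited and when; parents and physicians decide the rest.
- *A nurse chooses the number.* Numbers follow the order in which consent is signed, so the text leaves no choice.
- *Exclusion c gives these nurses discretion.* Its wording, "other factors which indicate exclusion in the judgment of the study staff", is broad, but 10.6.3 F gives the exclusion criteria to the investigator, and 10.6.6 E has the investigator decide that a parent cannot manage the diary.
- *No analysis could detect the resulting imbalance.* Birth date, history, weight, height and a day-0 blood sample are collected from every child (10.6.1, Table 5), so imbalance in recorded factors could be seen and adjusted for. Only unrecorded factors would escape.

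None of the safeguards separates the people who invite from the people who know past allocations.

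**Conclusion.** The concern holds as an opportunity for selection bias that the plan leaves open. Its ceiling is about 19 to 20% of allocations known with certainty and about 56% guessed correctly, against 33% by chance. The ceiling assumes a nurse who sees or learns every allocation and knows the block size. The true figures would be lower, by an amount that the documents do not allow one to estimate. The protocol does not show that selection occurred or would occur. The change is still worth making: the sponsor already treats block counting as a threat, the measure taken against it is weak against the staff who open the envelopes, and the gap can be closed with little effort.

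**What to change.** State in 10.6.3 A and 10.4.4 that anyone who acts as injection nurse or holding assistant does not identify or invite participants. Do this by dividing the nurses in 10.6.2 into two fixed groups. The list gives five registered and three auxiliary nurses, so at least eight. Have a blinded physician record the consecutive ID number when consent is signed, which keeps the existing order rule.

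If the roster cannot be fully divided, have the independent party use randomly varying block sizes in multiples of three, not disclosed to the site, in place of the single split block. This reduces predictability but does not remove it.

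The main change costs a few sentences and less flexible shifts. Whether it needs no extra staff is an assumption: each injection already takes two unblinded people, and the protocol does not say how many nurses work each shift. The fallback costs slightly looser balance during enrolment, and the block size would have to come out of the protocol text held at the site.

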10.6.4 Informed Consent Process

The informed consent process will occur in the following steps:

A. The investigator will inform parents that participation requires their written consent and the content of the consent form will be explained verbally. The parents will be requested also to read the consent form themselves, as well. If they agree to participate, they are requested to sign and date it.

B. Parents will be given the opportunity separately to consent or decline long-term storage of leftover, unused specimens for future testing (sections 7.3 and 10.5.1.4). Declining long-term storage and future testing shall not bar participation in the study if otherwise consented.

C. Parents who do not wish to participate in the study or to sign its consent form will be thanked for their time and interest and escorted or directed back to the Healthy Children and Vaccination Service [immunization clinic], where they will be attended to, if needed, or resume their original position in the queue.

10.6.5 Monitoring of Informed Consent Process

A social worker from the office of social work at the HIRRC will silently observe the first two weeks (or longer, as needed) of the informed consent process, in order to identify any difficulties or misunderstandings. He or she will request voluntary informal interviews with a convenience sample of parents upon their completion of day 0 activities, or upon their return on days 2 or 7, to explore the parents's comprehension of the informed consent, and any lingering questions. The social worker will meet three times weekly during this period, or more frequently as needed, with the Dominican Investigators to provide feedback on any gaps or weaknesses perceived in the informed consent process, so that its verbal explanations and other processes may promptly be revised or improved, if necessary.

HIRRC/CDC Needle-free Intradermal	Page 92	File: 4785-ID-INF-Prot-Engl-2008Jun24.doc
Influenza Study - CDC-ISO-4785	of 138	2008-Jun-24

10.6.6 Parent Training Procedure

Both in the Dominican Republic and the U.S., the filling out of diaries by parents to record vaccination-related observations at home are a common and accepted procedure. In the years 2002 through 2006 alone, the HIRRC itself collaborated in three multicenter studies with international pharmaceutical manufacturers on studies meeting current good clinical practice (cGCP). These required Dominican parents to record information daily at home about their child's illness following treatment for recent onset of middle ear infection (acute otitis media). In the United States, controlled, clinical trials of influenza vaccine have used parental diary cards to record information at home. Edwards1994, Belshe1998, Belshe2000

Parent training will occur, as follows:

A. While the physician investigator is conducting the physical examinations required in the CRF, he or she will explain in the parents presence how to perform those methods which they will repeat at home and record in the Diary form.

B. Before handing the Diary form to the parent, the investigator (or study nurses earlier) will prefill fields in the diary form for participant initials and ID number, study center telephone numbers, and the dates and days of the week at the top of Diary columns for recording reactions.

C. Using sample forms, the investigator will show and practice with the parents how to complete the Diary form. On the Day 7 visit, similar filling out and training will occur for the 7-28 day Diary form.

D. Specific skills the investigators and/or nurses will teach the parents include correct application, reading, and removal of the skin appliqué thermometer, use of the tape measure for limb circumference, and reading local reaction sizes using the plastic ruler/template.

E. Parents will be required to demonstrate actual use of these devices, and proper recording of the results in the form, in order to verify their understanding. Mistakes will require additional explanation until the parents can complete the form correctly, or the investigator determines that the parents are unable to do so and are excused from the study.

F. Parents will be provided with a study registration card with a photograph of the parent and child (to reduce the chance of mistaken identity on later visits). They will also receive an appointment card on which the days and hours of their next appointment will be written. Both cards will contain the telephone numbers to be contacted at any hour if any questions or concerns arise.

G. Parents will be provided with a take-home, closable notebook and/or satchel to carry their registration and appointment cards, the ruler/template and circumference tape, additional skin thermometers for replacing every two days, a signed copy of the informed consent and its accompanying additional information handout, plus the

HIRRC/CDC Needle-free Intradermal	Page 93	File: 4785-ID-INF-Prot-Engl-2008Jun24.doc
Influenza Study - CDC-ISO-4785	of 138	2008-Jun-24

parental Diary form to be used until day 7 (on that day, it will be replaced with another for the period from day 7 to 28).

H. The importance will be explained to the parents for their correctly completing the Diary form each day, and bringing the child back on days 2 and 7 and 28 after vaccination to be evaluated by the doctor.

I. After completion of the parent training and related forms, the study staff will undertake the venipuncture.

